6. STUDY PROCEDURES

6.1. Information Statement and Consent Form

Subjects who are identified as potentially suitable to participate in the study will be sent an information statement and consent form as approved by the Sponsor and by the Human Research Ethics Committee (HREC). The consent form will describe the purpose of the study, the procedures to be followed, and the risks and benefits of participation.

The screening visit will provide an additional opportunity for the subject to discuss any questions that they may have with study staff. Study staff are responsible for ensuring that the subject receives adequate information, and all questions are answered appropriately. Additionally, study staff must ensure subjects comprehend the information provided about the study, including a decision to participate will not impact usual medical care, and subjects retain an absolute right to withdraw at any time for any reason. If, after this discussion, the subject still wishes to enroll, the staff member that conducts the consent discussion will ensure that the consent is documented appropriately.

Documentation of consent must be obtained before any study-specific procedures are performed. A copy of the signed consent form will be given to the subject. The date that consent was obtained will be recorded in the electronic case report form (eCRF) as well as the subject's chart. Following documentation of consent, the subject will be allocated a screening number and will undergo screening assessments as indicated in [Appendix 1](#) and [Appendix 2](#) to ensure eligibility.

6.2. Randomization

On Day -1, the inclusion/exclusion criteria will be reviewed with the subject. A urine pregnancy test will be performed for WOCBP and subjects will be screened for drugs of abuse via a test panel upon admission (Day -3). Prior and concomitant medications will be reviewed. Any AEs since the signing of the informed consent will be collected. Please also refer to [Appendix 1](#) and [Appendix 2](#).

If the subject still meets study criteria, they will be randomized prior to dosing.

6.3. Demographic and Baseline Characteristics

Demographic data and other baseline characteristics will be recorded, including date of birth or age, gender, self-reported race and/or ethnicity, and smoking status of the subject. A standard medical, medication, and surgical history will be obtained with review of the selection criteria with the subject.

A medical history will be collected during screening using forms designed to capture, at a minimum, the parameters specified by the protocol and to be recorded in the study case report form (CRF). Medical history includes an assessment of past and present clinically significant diseases and surgeries or important medical events (any within the past year). Additionally, an assessment of current reproductive status will be collected.

Record all medications (e.g., prescription and OTC medications, hormonal birth control, herbal or homeopathic remedies, and nutritional supplements) used by the subject within 30 days prior to the screening visit.

Ongoing medical status will also be reviewed at each study visit to screen for and capture AEs.

6.4. Physical and Neurological Examinations

A medical assessment will be completed by the principal investigator (PI) or a study physician at study entry, and at any early withdrawal visits. The primary purpose of the medical assessment at study entry is to confirm the subject's suitability to enroll in the study.

The physical examination will include height (screening only), body weight, and an evaluation of the head, eyes, ears, nose, and throat, and the cardiovascular, dermatological, musculoskeletal, respiratory, gastrointestinal, and neurological systems. Record any abnormality identified prior to administration of study medication as medical history.

Any clinically significant, new, or worsened abnormalities that occur after administration of study medication should be recorded as AEs. Additional parameters may be assessed as indicated by any subject symptoms.

Abbreviated physical examinations performed throughout the study should be symptom-directed.

Neurological examination shall include assessment of cranial nerves, motor, sensation, coordination, reflexes, and gait. Abbreviated neurological examinations performed throughout the study include light touch/power in limbs and brief cranial nerve examination.

Findings will be recorded as normal/abnormal for each parameter with additional description as indicated. All abnormal, clinically significant, findings will be considered AEs.

Please refer to the Schedule of Assessments (SOA) in [Appendix 1](#) and [Appendix 2](#) for details regarding timing for assessments.

6.5. Vital Signs

Vital signs will be recorded at screening, study entry, and at all visits before and after dosing of study drug, including:

- body temperature,
- respiratory parameters (including respiratory rate, saturated oxygen, pulse oximetry),
- pulse rate,
- heart rate (after 3-minute semi-supine rest), and
- arterial blood pressure (systolic and diastolic; after 3-minute rest in either a semi-supine or sitting position).
- peak flow measurement.

During the inpatient dosing period, vital signs also include respiratory rate, continuous pulse oximetry and saturated oxygen, which will be undertaken via telemetry within 2 hours predose and at 2 hours postdose (\pm 15 minutes) as per the schedule in [Appendix 1](#) and [Appendix 2](#). For MAD Cohort 3, vital signs, including telemetry will be conducted following each dose (am and pm).

Peak flow measurement will also be undertaken within 1 hour predose as well as at 1-, 2-, and 4-hours (\pm 15 minutes) postdose. For MAD Cohort 3, peak flow measurements will be conducted following each dose (am and pm). The highest of 3 peak flow measurements, at each timepoint shall be recorded.

Protocol Exclusions 2 and 3 pertaining to vital signs should be checked at both Screening and Day -1 to confirm eligibility. Following the Day-1 eligibility check, any subject with vital signs outside of acceptable range will have their vital signs repeated. If the readings are again abnormal, but not clinically significant, it is at the PI's discretion as to whether to continue the subject in the study. Normal vital sign ranges for this study are presented in [Appendix 4](#).

For details regarding timing for assessments, please refer to the SOA in [Appendix 1](#) and [Appendix 2](#).

6.6. Gastrointestinal Symptoms

Changes in gastrointestinal function will be monitored during the MAD part of the study. Bowel movements, such as constipation, and any change in bowel habits as reported by study subjects will be recorded daily during the dosing period.

Please refer to the SOA in [Appendix 2](#) for details regarding timing for these assessments.

6.7. Columbia Suicide Severity Rating Scale (C-SSRS)

The C-SSRS is a questionnaire used for suicidality assessment developed by multiple institutions, including Columbia University. The scale is evidence-supported and is part of a US national and international public health initiative involving the assessment of suicidality. The scale has been successfully implemented across many settings, including schools, college campuses, military, fire departments, the justice system, primary care and for scientific research. The C-SSRS Risk Assessment version is intended to help establish a person's immediate risk of suicide and is used in acute care settings.

The C-SSRS will be administered at screening and again at Day 4 and Day 7 postdose during the MAD part of the study. Please refer to the SOA in [Appendix 2](#) for details regarding timing for assessments.

6.8. Concomitant Medications

Concomitant medications will be assessed at each study visit by staff discussion with the study subjects. For any concomitant medications not otherwise linked to reported AEs, staff should discuss with the subject to clarify the indication for medication.

Refer to [Section 5.9](#) for information on prior and concomitant medications, including those that must be halted within defined time periods prior to randomization.

Please refer to the SOA in [Appendix 1](#) and [Appendix 2](#) for details regarding timing for assessments.

COVID-19 vaccinations will be permitted if they occur more than 14 days before the treatment period or after the EOS visit.

6.9. Contraception

WOCBP must have a negative serum or urine pregnancy test within 24 hours prior to the start of study drug and must not be breastfeeding, lactating, or planning pregnancy during the study period. WOCBP are defined as any female who has experienced menarche and who has not undergone surgical sterilization (hysterectomy or bilateral oophorectomy) and is not postmenopausal. Menopause is defined as 12 months of amenorrhea in the absence of other biological causes. In addition, females under the age of 55 years must have a documented serum follicle stimulating hormone (FSH) level > 40 mIU/mL to confirm menopause. Male participants with potentially postmenopausal partners who are under the age of 55 years must use condoms unless their partner's postmenopausal status has been confirmed by FSH level.

WOCBP who are not exclusively in same-sex relationships and males with partners of child-bearing potential must agree to use adequate contraception. For WOCBP, contraception should be continued for 30 days after the final study visit. For males, contraception should be continued for 90 days after the final dose of study drug. In addition, males must not donate sperm for 90 days after the final dose.

Males and WOCBP who are continuously not heterosexually active are exempt from contraceptive requirements. However, WOCBP must still undergo pregnancy testing as per protocol.

Investigators will counsel WOCBP and male participants who are sexually active with WOCBP on the importance of pregnancy prevention and the implications of an unexpected pregnancy. Investigators will advise on the use of an adequate methods of contraception, which is defined as use of a condom by the male partner combined with use of a highly effective method of

contraception by the female partner. A highly effective method of contraception is one that has a failure rate of <1% when used consistently and correctly. Male participants must inform their female partners who are WOCBP of the contraceptive requirements of the protocol and are expected to adhere to using contraception with their partner.

Highly effective methods of contraception are listed below:

- Hormonal methods of contraception including oral contraceptives containing combined estrogen and progesterone, a vaginal ring, injectable and implantable hormonal contraceptives, intrauterine hormone-releasing system (e.g., Mirena) and progestogen-only hormonal contraception associated with inhibition of ovulation.
- Nonhormonal intrauterine device (IUD)
- Bilateral tubal occlusion
- Vasectomized subject/partner with documented azoospermia 90 days after procedure if that partner is the sole sexual partner.

For female participants, hormonal contraceptives should begin at least 1 month prior to screening to ensure contraceptive is in full effect.

Complete abstinence, defined as the complete avoidance of heterosexual intercourse, is an acceptable form of contraception if used consistently throughout the duration of study and for the durations after dosing specified for males and females above. It is not necessary to use any other method of contraception when complete abstinence is elected. WOCBP who choose complete abstinence must continue to have pregnancy tests as per protocol. The reliability of sexual abstinence needs to be evaluated by the investigator in relation to the duration of the clinical study and the preferred and usual lifestyle of the subject.

6.10. 12-Lead Electrocardiograms

12-lead ECGs will be used to evaluate heart rate, atrial ventricular conduction, QRS and QT intervals, and possible arrhythmias. ECGs include ventricular heart rate; QRS duration; PR, RR, QT, QTcB, and QTcF intervals; and P and T wave. Evaluations will be recorded as normal, abnormal (not clinically significant), or abnormal (clinically significant).

The 12-lead ECGs will be obtained after the subject has been resting semi-supine for at least 3 minutes prior to the indicated times. All ECGs should be recorded with the subject in the same physical position. For each time point, 3 ECG recordings should be taken at approximately 1 to 3-minute intervals.

A standardized ECG machine should be used, and the subject should be tested using the same machine throughout the study, if possible. When the timing of these measurements coincides

with a blood collection, obtain the ECG prior to the nominal time of the blood collection, blood pressure, and heart rate.

Additional ECGs should also be collected if a subject experiences a cardiac AE.

After ECGs have been recorded, the PI or a designated physician will review each of the ECGs. If available, a paper copy should be filed in the subject's medical records. For all ECGs, ECG intervals and an overall assessment will be recorded. Evaluations will be recorded as normal, abnormal (not clinically significant), or abnormal (clinically significant).

For details regarding timing for assessments, please refer to the SOA in [Appendix 1](#) and [Appendix 2](#).

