13. Subjects with a history of chronic alcohol (regular daily intake of more than three standard drinks) or drug abuse within the last 6 months prior to first administration, or evidence of such abuse as indicated by the laboratory profile conducted during the screening examination.
14. Subjects who have received prescription drugs or over-the-counter (OTC) medication including dietary supplements, COVID-19 vaccine, standard dose vitamins, or herbal products within 14 days prior to the first administration (with the exception of the oral contraceptive pill).
15. Subjects who received any treatment agents known to alter the major organs or systems within 30 days prior to the first administration (e.g., diuretics, nephro- or liver toxic medication, barbiturates, phenothiazines, cimetidine, more than 1.0 L of caffeine-containing beverages per day, etc.).
16. Diagnosed infection of any kind, e.g., viral, bacterial, fungal, or mycobacterial within 1 month prior to the first dose of KNX100 or current fever or clinical signs or symptoms of infection at screening or Day -1.
17. Treatment with an unapproved investigational therapeutic agent within 30 days (or 5-half-lives for small molecule agents) prior to the first dose of KNX100.
18. Females who are pregnant (positive pregnancy test at screening or prior to first dose), lactating or unable/unwilling to use defined methods of contraception throughout the study.

Laboratory assessments conducted at screening for any exclusion criterion may be repeated once to rule out a laboratory error. Only the value leading to inclusion of the subject will be recorded. Vital signs recorded outside the exclusion criteria ranges may also be repeated once for confirmation.

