6.13. Clinical Laboratory Tests

Subjects will be required to fast overnight prior to collection of Clinical Laboratory Samples.

All subjects undergo screening via a blood test to rule out human immunodeficiency virus (HIV), Hepatitis B and C.

Serum human chorionic gonadotrophin will be determined in WOCBP at screening. A urine pregnancy test will be conducted in WOCBP upon admission (Day -3).

Urine will be collected for drug screening as well as urinalysis. Urinalysis will be assessed by dipstick analysis. Microscopic examination will be undertaken if there is an abnormality warranting further investigation.

An alcohol breath test will be conducted at Screening to determine eligibility.

Blood samples will be collected for hematology and serum chemistry as well as coagulation parameters.

Subjects will be in a seated or supine position during blood collection. A list of the clinical laboratory tests is provided in [Appendix 5](#). Please refer to the SOA in [Appendix 1](#) and [Appendix 2](#) for details regarding timing for assessments.

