Appendix 1 Schedule of Assessments - SAD

	Screening	Treatment			Follow Up/ ET/EOS ¹
Study Day	-28 to -2	-1	1	2 ²	7 (±2)
Informed Consent	X				
Inclusion/Exclusion Criteria ³	X	X			
Randomization ⁴		X			
Height and BMI	X				
Medical History and Demographics	X				
Physical and Neurological Exam ⁵	X	X	X	X	X
Vital Signs ⁶	X	X	X	X	X
Laboratory Tests ⁷					
Serology	X				
Hematology	X	X	X	X	X
Serum Chemistry	X	X	X	X	X
Urinalysis ⁸	X	X	X	X	X
Coagulation	X	X	X	X	X
Pregnancy Test ⁹	X				X
Drug of Abuse Screening ¹⁰	X	X			
Alcohol Breath Test	X				
Study Drug Administration ¹¹			X		
PK Assessments ¹²			X	X	
Biomarker Sample ¹³		X	X		X
EEG ¹⁴	X		X	X	
12-Lead ECG ¹⁵	X	X	X	X	X
Adverse events	X	X	X	X	X

	Screening	Treatment			Follow Up/ ET/EOS ¹
Concomitant Medications	X	X ³	X	X	X
Inpatient Component ¹⁶	X	X	X	X	

Abbreviations: BMI = body mass index; ECG = electrocardiogram; EEG = electroencephalography; ET = early termination; EOS = end of study; PK = pharmacokinetics; SAD = single ascending dose.

¹ All subjects will be required to attend an ET/EOS visit, even if they have withdrawn or been removed from the study. For completed subjects, this will be at Day 7.

² For sentinel subjects this will include a follow up phone call at 48 hours.

³ Confirmation of eligibility based on inclusion/exclusion criteria.

⁴ Randomization to occur after confirmation of eligibility on Day -1 and prior to dosing on Day 1.

⁵ An abbreviated neurological examination will be undertaken to include: light touch/power in limbs, brief cranial nerve examination and recording of any other abnormal movements; to occur on Day-1, Day 1 predose and at 30 minutes (\pm 15 minutes) postdose, and Day 2. Physical and neurological examination on Day 2 should be performed pre-discharge.

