⁶ Vital signs collection includes systolic and diastolic blood pressures, pulse rate and body temperature which will be measured with the subject to be seated or semi-supine after resting for at least 3 minutes. Vital signs also include respiratory rate, continuous pulse oximetry and saturated oxygen, which will be undertaken via telemetry within 2 hours predose and at 30 hours (\pm 30 minutes) after dosing. Measurements of all vital signs will be recorded within 1 hour predose, and at 30 minutes, 1-, 1.5-, 2-, 4-, 6-, 8-, 12-, 24- and 30-hours postdose (\pm 15 minutes). Peak flow measurement will also be undertaken within 1 hour predose as well as at 1-, 2-, and 4-hours (\pm 15 minutes) postdose. The highest of 3 peak flow measurements, at each timepoint, shall be recorded.

⁷ Subjects should fast overnight prior to collection of laboratory tests at Screening. The Day 1 laboratory tests will be undertaken at 1 hour postdose (\pm 15 minutes) and at 24 hours (\pm 15 minutes) postdose (Day 2).

⁸ The Day 1 urinalysis tests will be undertaken at 1-hour postdose (\pm 60 minutes) and at 24 hours (Day 2) (\pm 60 minutes) postdose.

⁹ Serum pregnancy test at Screening and End of study visit. A urine pregnancy test will be conducted in women of child-bearing potential on admission to unit on Day -3.

¹⁰ Test may be repeated if required.

¹¹ Each subject will receive study drug based on randomization (placebo or KNX100), after a 10 hour fast.

¹² Please refer to [Appendix 3](#) for information related to PK assessments and sampling times.

¹³ Plasma samples for biomarker analyses will be collected predose (Day -1), on Day 1 at 1-hour postdose (\pm 15 minutes), and at EOS/EOT.

¹⁴ EEG: Please refer to [Appendix 3](#) for information related to EEG assessments.

¹⁵ Please refer to [Appendix 3](#) for information related to ECG assessments which will be performed in triplicate. The timing and number of ECGs may be altered, depending on the emerging PK and safety profile. Additional ECGs should also be collected if a subject experiences a cardiac adverse event.

¹⁶ Participants will be admitted to the Phase 1 unit on Day -3 so they can sleep for 4 hours prior to undertaking their sleep deprived EEG on Day -2, through to 30 hour testing on Day 2.

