⁷ Vital signs will be measured with the subject to be seated or semi-supine after resting for at least 3 minutes. Measurements will include systolic and diastolic blood pressures, pulse rate, body temperature, respiratory rate, saturated oxygen and pulse oximetry which will be recorded via telemetry within 2 hours predose and at 2 hours postdose (± 15 minutes). Peak flow measurement will also be undertaken within 1 hour predose as well as at 1-, 2-, and 4-hours (± 15 minutes) postdose. The highest of 3 peak flow measurements, at each timepoint, shall be recorded. For MAD Cohort 3, vital signs, telemetry, and peak flow measurements will be recorded following each dose as per the schedule above.

⁸ Laboratory tests will be undertaken as depicted above. The Day 1 laboratory tests will be undertaken 1 hour post morning dose (± 15 minutes).

⁹ A serum pregnancy test will be undertaken at screening and End of Study visit. A urine pregnancy test will be conducted in women of child-bearing potential on admission (Day -3).

¹⁰ Drug abuse screening and alcohol breath test will be conducted at admission (Day -3).

¹¹ Subjects in Cohorts 1 and 2 of the MAD study phase will be dosed daily for 7 days at approximately the same time each day. Each subject will receive study drug based on randomization (placebo or KNX100), after a 10 hour fast. Subjects will remain fasted until 2 hours (±15 minutes) post study drug administration.

Subjects in Cohort 3 of the MAD study phase will be dosed twice daily (b.i.d) with doses administered approximately 8 hours (\pm 30 minutes) apart. The first dose will be administered following a 10 hour overnight fast, and subjects will remain fasted until 2hours (\pm 15 minutes) post study drug administration. Subjects will be required to fast 2 hours (\pm 15 minutes) prior to administration of the second dose of study drug and will remain fasted until 2hours (\pm 15 minutes) post study drug administration.

¹²Please refer to [Appendix 3](#) for information related to PK assessments and sampling times. The timing and number of PK samples may be altered depending on emerging data and safety profile. Please note, Day 4 predose sample is not required for Cohort 3.

¹³ Plasma samples for biomarker analyses will be collected predose (Day -1), and 1 hour post morning dose (\pm 15 minutes) on Days 1, 2, 3, 7 and at the ET/EOS visit.

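### The pre-dose pregnancy test is scheduled on Day -3, outside the protocol's own 24-hour limit in Part A, and Part B gives two different days for it

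*Protocol*

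**What the plan says.** Protocol Section 6.9 sets the rule: "WOCBP must have a negative serum or urine pregnancy test within 24 hours prior to the start of study drug".

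The timing is given in five other places:

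- **Section 6.13 (both parts):** "A urine pregnancy test will be conducted in WOCBP upon admission (Day -3").
- **Appendix 1 (Part A, single dose), footnote 9:** "A urine pregnancy test will be conducted in women of child-bearing potential on admission to unit on Day -3". The grid row marks only the screening and follow-up columns.
- **Appendix 2 (Part B, multiple dose), footnote 9:** "A urine pregnancy test will be conducted in women of child-bearing potential on admission (Day -3"). The grid row, however, marks screening, Day -1 and end of study.
- **Section 6.2:** the paragraph opens with the Day -1 eligibility review and continues "A urine pregnancy test will be performed for WOCBP and subjects will be screened for drugs of abuse via a test panel upon admission", with Day -3 in brackets after it.
- **Exclusion criterion 18 (Section 4.3):** "Females who are pregnant (positive pregnancy test at screening or prior to first dose"), with no day or hour limit.

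**The concern.** A mandatory safety rule in the body of the protocol is not carried into the schedule of assessments, which is what a site commonly works from. In Part A no scheduled test can satisfy it. In Part B the grid and its footnote name different days, and only one of those days could satisfy it.

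This is a first-in-human study, and the 24-hour test is the last check on pregnancy that the protocol sets for itself. A site that follows the footnotes and adds nothing will dose WOCBP outside the window. Section 9.9 requires each such departure to be recorded as a deviation. No endpoint or sample-size figure depends on this. The stake is participant protection and avoidable deviations.

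**Working it through.** **Inputs**

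- Limit: 24 hours from negative test to first dose (Protocol 6.9).
- Scheduled urine test: Day -3 (Protocol 6.13; Appendices 1 and 2, footnote 9).
- Day numbering: the SAP 5.2 study-day formula has no Day 0, so the sequence is Day -3, -2, -1, 1. Day -3 is 3 calendar days before dosing and Day -1 is 1 day before.
- Dose time: morning in Part A (Protocol 5.3.2); 11:00 as an example in Part B (Protocol 5.3.3).

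**Formula**

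Age of test at dosing (hours) = 24 × (calendar days from test to Day 1) + (dose clock time − test clock time).

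**Age of a Day -3 test**

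| Case | Arithmetic | Age |
|---|---|---|
| Same clock time | 24 × 3 + 0 | 72 h |
| Lower bound, any clock times | end of Day -3 to start of Day 1 | more than 48 h |
| Upper bound, dose before noon | 72 + (12 − 0) | less than 84 h |
| Dose at 11:00 | 72 + 11 − 24 to 72 + 11 − 0 | 59 to 83 h |

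The excess over the limit is at least 48 − 24 = 24 h, and nominally 72 − 24 = 48 h.

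**Could the screening serum test rescue Part A?** The screening column ends on Day -2. From the last minute of Day -2 to the start of Day 1 is 24 h, so even a test then would be more than 24 h old at a morning dose.

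**Part B, grid against footnote.** Footnote 9 names three tests: serum at screening, serum at end of study, and urine at admission on Day -3. The grid row has three marks: screening, Day -1 and end of study. Matched one to one, the Day -1 mark is the Day -3 urine test. The drug-screen and alcohol marks in that same column are treated this way explicitly by footnote 10: "Drug abuse screening and alcohol breath test will be conducted at admission (Day -3"). Read like that, Part B misses the window as Part A does.

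Read instead as a true Day -1 test, the mark carries no clock time. With an 11:00 dose its age would run from 24 + (11 − 24) = 11 h to 24 + (11 − 0) = 35 h. It complies only if taken no earlier than 11:00 on Day -1.

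**Subjects planned.** Part A: 4 cohorts × 8 = 32. Part B: 3 cohorts × 8 = 24.

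**The case against.** The strongest reply is that Section 6.9 is worded as an obligation and is the stricter instruction, so it governs. The Day -3 test does not forbid a later one, subjects are resident from Day -3, urinalysis is already scheduled on Day -1 in both parts, and eligibility is re-confirmed that day. A careful site would add the test. That is fair, but it relies on the site noticing a rule that the schedule does not implement.

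For Part B, the drug and alcohol marks carry the redirecting footnote on the mark itself, whereas the pregnancy mark does not. It could therefore be an additional Day -1 test, and doing both would satisfy every instruction. This reading is possible, so Part B is better called conflicting than proven non-compliant. It does not remove the conflict, because footnote 9 gives the row's only urine test to Day -3.

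Three further points stand:

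- The 24-hour window is not an entry criterion, since exclusion 18 sets no window. A missed window alone is a recorded deviation and not one of the entry-criteria violations listed in Section 9.9.
- The 32 and 24 include men and women who are not of childbearing potential.
- Section 3.2.1 shows that dosing had begun, so an amendment cannot reach subjects already treated.

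**Conclusion.** The concern holds. In Part A the last scheduled pregnancy test before dosing is more than 48 hours old, nominally 72, against a limit of 24. In Part B the grid and footnote disagree, and neither reading assures a test inside the window. Section 6.2 does not settle the matter because it mixes Day -1 and Day -3, and exclusion 18 is met by a negative Day -3 test.

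The WOCBP among 32 planned Part A subjects have no scheduled in-window test; those among 24 planned Part B subjects fall under the conflicting instruction. The documents do not give the number of WOCBP. The time bounds rest on the SAP day numbering and, for the upper figure, on a dose before noon.

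The added risk is small: the screening serum test, the Day -3 urine test, contraception and continuous residence remain. The inconsistency should still be corrected, because following the footnoted schedule as written breaks a stated safety rule.

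**What to change.** Schedule a urine pregnancy test for WOCBP in both grids and both footnotes, at one of two times:

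- **Day -1, within 24 hours of the planned dose.** The result can be read before randomization, and the Day -1 urinalysis sample can serve if it falls in the window. If dosing slips past 24 hours, repeat the test predose.
- **Predose on Day 1.** This always meets the limit. Appendix 1 footnote 4 reads "Randomization to occur after confirmation of eligibility on Day -1 and prior to dosing on Day 1", so the test can be placed ahead of randomization. If a positive result comes after randomization, Section 5.4 already allows a replacement.

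Align Sections 6.2 and 6.13 with the chosen time. Keep the Day -3 test if wanted, labelled as an admission check.

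The cost is wording and table edits in the next amendment and one urine strip per WOCBP. If the sponsor considers the Day -3 test sufficient, the alternative is to amend Section 6.9, but the two statements cannot both stand.
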